Church-based Health Advisors and our Health Practitioner to Deliver Seminar and Workshop (Phase 2): The bi-weekly seminars will be peer-led and conducted by each church-based health educator within their church. In each seminar, one of our specialists will participates in delivering the main component of intervention. For example, the infectious disease expert will help individuals reduce the risk of acquiring COVID-19; the pharmacist will work with participants to enhance their medication adherence and remove barriers related to their refills; and the lifestyle coach will help improve participants' lifestyles; etc.

Hypotheses: As a result of this intervention, it is expected that: 1) A 30% improvement of chronic physical and mental disease management among AA older adults; 2) A 80% increase in knowledge, attitude, and behaviors of COVID risk among AA older adults; and 3) a 40% increase in COVID-19 testing and 4) a 70% increase in uptake of influenza and pneumococcal vaccinations among participants.

Survey Instruments: Per the instruction of this NOSI, we will adopt survey instruments recommended by the **phenX Toolkit and Public Health Emergency and Disaster Research Response**.¹¹⁴ The survey (developed by the Aging and Geriatric Research Institute on UF) includes Covid-19 related measures and Health status and health care utilization, quality of life, and other related variables. In addition, we will include several validated survey instruments that our research team has recently used among AA older adults to investigate health status, health care utilization, and adherence to drug regimes in South Los Angeles.

Sample Size and Data Analysis (Phase 2): We will use a pretest–posttest design, comparing our outcomes before and after the intervention, with a three-month interval. Since our outcomes are binary (COVID infection

status, use of services, medication non-adherence, etc.), we will use the McNemar test, the test of choice for analyzing binary matched-pairs data.¹¹⁵ For our power calculation, we assume that our primary outcome (poor adherence) will show a 36% relative change (considering a 22% baseline

TIMELINE: Activities & Timeline (Months)	1-3	4-6	7-9	10-12
Church leaders recruited	X			
CDC/States Guideline Implementation	X	X	X	X
Health Advisors recruited & trained	X	X		
AA older adults recruited		X	X	X
Baseline data collection (older AA)		X	X	X
IRBNet # 1663247-2 Approved by: CDU IRB				
Older AA Intervention implemented		X	X	

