Post intervention data collected & analyzed			X	X
Final reports & RO1 preparation				X

Approval Period: April 23, 2021 to

status). Assuming an alpha of 0.05, we calculate that a total sample of 240 study participants will be necessary to achieve 80% power.¹¹⁶ With 10% drop-out,^{117,118} we will need to enroll 265 individuals. We will conduct longitudinal follow-up assessments to document changes to compare with baseline measures. At the descriptive level, the distribution and frequency of all items will be examined. The main hypothesis of this study is significant improvement of binary and continuous outcomes from pre- to post- tests. In bivariate analysis, we will apply McNemar's test as well as paired t-test to examine improvement of the outcome over the course of the study. Conducting multivariate analysis, when outcome variables are dichotomous/binary, to explore the role of potential confounders and baseline health status, as determinants of response (change), we will apply logistic regression. However, for corresponding dependent variables that appear to be ordinal a logit link will be used in polytomous or ordinal logistic models. Additionally, for continuous outcomes, we will use GLM to determine statistical differences in the primary outcome measures, while controlling for potential confounders and covariates associated with the selected outcomes. It should also be noted that missing results over time will be accounted for in the analysis using an inverse probability weighting scheme based on a logistic regression model.

References:

4. Barrett RK. Dialogues in diversity: An invited series of papers, advance directives, DNRs, and end-of-life care for African Americans. *OMEGA-Journal of Death and Dying*. 2006;52(3):249-261.
6. Escher Jr AR. An Ounce of Prevention: Coronavirus (COVID-19) and Mass Gatherings. *Cureus*. 2020;12(3).

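### The sample size rests on one primary outcome, but the main hypothesis is an unlisted set of outcomes with no rule for multiplicity or success

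*Combined protocol and SAP*

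**What the plan says.** Two parts of the combined protocol and SAP bear on this.

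**Sample Size and Data Analysis (Phase 2).** The section opens by describing the outcomes as binary, gives three examples in a list that is left open, and chooses McNemar's test. The power calculation assumes that "our primary outcome (poor adherence) will show a 36% relative change" from a baseline of 22%. It continues: "Assuming an alpha of 0.05, we calculate that a total sample of 240 study participants will be necessary to achieve 80% power". Drop-out of 10% brings enrolment to 265.

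A few sentences later the same section says: "The main hypothesis of this study is significant improvement of binary and continuous outcomes from pre- to post- tests". McNemar's test and the paired t-test are to be used in bivariate analysis, followed by regression models. For continuous outcomes, "we will use GLM to determine statistical differences in the primary outcome measures".

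**Hypotheses.** Four numbered expectations are given, most of them compound; the second is "A 80% increase in knowledge, attitude, and behaviors of COVID risk among AA older adults". The others concern physical and mental disease management, COVID-19 testing, and uptake of two vaccines. None is called poor adherence.

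The level 0.05 appears once, in the power calculation, and its sidedness is not stated. The documents give no multiplicity adjustment and no testing order. They do not say whether success means one particular outcome, any outcome or all of them.

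**The concern.** A reader of the power calculation takes poor adherence to be the single confirmatory outcome. A reader of the main-hypothesis sentence takes the trial to stand or fall on a group of outcomes, some of them continuous, that is never listed. The GLM sentence points the same way, because a binary adherence variable cannot be one of the continuous primary measures it refers to.

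This goes beyond an omitted detail, since one stated rule contradicts another. At stake is what the final report may call its main result. Under the main-hypothesis sentence, a significant change in an outcome outside the power calculation could be reported as support for the main hypothesis. The 80% power applies to one test only, and the plan does not bound the false-positive rate for the whole set.

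**Working it through.** **Step 1: what the stated sample size covers.** The inputs from the power calculation are a 22% baseline, a 36% relative change, alpha 0.05 and 80% power. Read as a decrease, the follow-up proportion is 0.22 × 0.64 = 0.1408, a difference of 0.0792. A standard formula for McNemar's test is

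n = (z_α + 2 z_β √(pA(1 − pA)))² / (4 (pA − 0.5)² pD),

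where pD is the proportion of discordant pairs and pA is the share of those pairs in the favoured direction. The plan does not give pD, so 240 can be checked only over a range. Two-sided results by within-person correlation are:

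| Correlation | n |
|---|---|
| 0 | 366 |
| 0.2 | 292 |
| 0.3 | 254 |
| 0.4 | 216 |
| 0.5 | 178 |

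The value 240 is reached at a correlation of about 0.34. There pD = 0.2014 and pA = 0.1403/0.2014 = 0.697, so n = (1.960 + 0.774)² / (4 × 0.1966² × 0.2014) = 240. With a one-sided test it is reached at a correlation of about 0.16. For enrolment, 240/0.90 = 267 and 240 × 1.10 = 264, so 265 is consistent. The stated size is therefore attainable under an unstated discordance, and it covers one test of one outcome.

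**Step 2: the two descriptions side by side.**

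| | Power calculation | Main hypothesis and GLM sentences |
|---|---|---|
| Number of outcomes | One, named | Several, unlisted |
| Type | Binary | Binary and continuous |
| Level | 0.05 | Not stated |
| Success rule | Implied by the single test | Not stated |

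**Step 3: the error rate if any one success counted.** This step needs three assumptions that are not in the plan: each outcome is tested at two-sided 0.05, one success is enough, and the outcomes are independent. For k outcomes the chance of at least one significant result in either direction is 1 − 0.95^k. Counting only false improvements, it is 1 − 0.975^k.

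| k | Source of k | Improvement only | Either direction |
|---|---|---|---|
| 2 | smallest plural set | 4.9% | 9.8% |
| 3 | binary outcomes given as examples | 7.3% | 14.3% |
| 4 | numbered hypotheses | 9.6% | 18.5% |
| 8 | components of those hypotheses (2 + 3 + 1 + 2) | 18.3% | 33.7% |

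For k = 4: 1 − 0.975⁴ = 0.096 and 1 − 0.95⁴ = 0.185. The reference values for a single test are 2.5% and 5%. If the tests were one-sided at 0.05, the last column would be the improvement-only rate.

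**Step 4: correlated outcomes.** Simulated, equally correlated test statistics for four outcomes give 7.9% (improvement only) and 15.7% (either direction) at correlation 0.5, and 4.6% and 9.3% at 0.9.

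**Step 5: the other success rules.** If every outcome had to be significant, the error could not exceed the level of one test, 5%. If only poor adherence is confirmatory, it is 5%.

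**The case against.** The strongest reply is that the primary outcome is fixed. Poor adherence is named in the singular, with a baseline rate, an effect size and a test, and the enrolment target follows from it. Moving to another primary outcome would be a visible departure from that text. The plural in the GLM sentence occurs in a passage about covariate adjustment and may be loose wording. The four numbered hypotheses are expected percentage changes with no test or level attached.

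Much of this stands, and it rules out some stronger readings. A reader might infer that every outcome is tested at 0.05, but that level is given only for the power calculation; extending it is a natural default and not a statement in the plan. A reader might infer that any one significant outcome establishes the main hypothesis. No such rule is written, and the sentence can equally be read as requiring improvement throughout. A reader might also infer that the primary outcome is free to be picked once results are known, which overlooks the power calculation.

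The reply does not remove the conflict. The main-hypothesis sentence is explicit, it includes continuous outcomes, and it does not mention poor adherence. Nothing in the documents says which of the two statements governs.

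**Conclusion.** The concern holds as an internal contradiction that should be resolved before analysis: one outcome carries the sample size and power, while the main hypothesis is an unlisted set with no multiplicity or success rule.

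The size is conditional. If any one improvement counted and four independent outcomes were each tested at 0.05, the false-positive chance would be about 10% (two-sided tests, false improvements only) to 19% (either direction). At correlation 0.5 it would be about 8% to 16%. If all outcomes had to succeed, it would not exceed 5%.

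The documents do not support the statement that the error rate is far above 5%, or above 5% whenever one success is enough. Two independent outcomes, improvement only, give 4.9%, and four highly correlated ones give 4.6%. The higher figures of 18.5% to 33.7% count significant worsening as success if the tests are two-sided. The number of outcomes, their correlation, the sidedness and the success rule are all unstated. These calculations address multiplicity only, not bias from the uncontrolled pre-post design.

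**What to change.** In Sample Size and Data Analysis (Phase 2):

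- Rewrite the main-hypothesis sentence so that the main hypothesis is a reduction from baseline to three months in the proportion with poor adherence, tested once by McNemar's test at two-sided 0.05. Say which adherence measure is meant, since Table 1 lists several adherence behaviours.
- Label all other outcomes, including the four numbered hypotheses, as secondary or exploratory, and report them as estimates with 95% confidence intervals. A multiplicity procedure such as Holm's is optional, if formal secondary claims are wanted.
- In the GLM sentence, refer to continuous secondary outcomes in place of primary ones.
- Reconcile the opening description of the outcomes as binary with the later inclusion of continuous ones.

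The cost is a few sentences. Secondary outcomes can no longer support the main claim. Power for poor adherence and the 240/265 sample size are unchanged, provided that the 0.05 in the power calculation was two-sided. Keeping four co-primary outcomes would cost more: at a Bonferroni level of 0.05/4 = 0.0125, and with the discordance that yields 240, the poor-adherence test alone would need about 344 analysable participants.
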